There are numerous potentially beneficial stress-reduction strategies that have been found to help college students effectively deal with stress and its negative health consequences worldwide [10]. Benson's (1975) relaxation response hypothesis states that all stress-reduction techniques have the same impact on health outcomes through evoking similar relaxation responses. Based on the relaxation response hypothesis, relaxation trainers are often contented to apply one general approach to relaxation to all clients. However, the specificity theories of relaxation claim that each approach of relaxation is associated with different health benefits [11,12]. For example, PMR, classified as somatic technique, works better to improve physical health. Guided imagery is more effective in improving emotional health. Mindfulness meditation is categorized as a cognitive technique, which should work better for improving cognitive health. These benefits of all relaxation techniques are mediated by increased parasympathetic activity [11]. However, research offers conflicting support for this notion. This study will investigate and compare the empirically defined effects of three common mind-body modalities, including progressive muscle relaxation (PMR), guided imagery, (GI) and mindfulness meditation (MM), on cognitive, emotional and physical health in nursing students. In other words, this study is an attempt to rigorously map the emotional, physical, and cognitive effects of these mind-body modalities among Jordanian nursing students.

Significance of Study

Despite the potential benefits of using PMR, GI, and MM, their effects have not been studied among Jordanian nursing students. Specifically, the current study intends to offer information about the effect of PMR, GI, and MM on health outcomes in the target population. Practically, results from the study may inform the decision-making of faculty and administrators about adopting PMR, GI, and MM in nursing colleges. The expected results will hopefully give clinicians and relaxation trainers tools for intelligently tailoring

techniques to students based on stress symptoms or health problems they experience [13]. Theoretically, the current study also extends the body of nursing knowledge and fill the theoretical gap in the literature regarding the effects of PMR, GI, and MM on health in nursing students and potentially support specificity theories of relaxation.

Methods

Design

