Statistical analysis will be conducted using SPSS software (version 23). Descriptive statistics will be used to describe the sample. The sample and variables will be described by measures of central tendency and dispersion appropriate to the level of measurement. Initial analyses will be conducted to ensure that the randomization across covariates was successful. The gender, marital status, employment, nationality, and smoking behavior variables will be all tested at baseline using Chi-square to demonstrate that they are not significantly different

between groups. Independent t-tests will be run at baseline measurements of dependent variables to make sure the study groups will be not significantly different on these variables before introducing the study intervention. One-way- ANOVA will be used to test the study hypotheses. Post hoc t-tests will be run to examine if the study groups will be significantly different on the dependent variables at end of the intervention. In case of having confounding effects of some variables, ANCOVA will be used.

Ethical consideration

Physical or psychological harm or risks that might be associated with the measurement activities or intervention employed in the current study will be minimal. One risk that might have resulted from the study was making demands on the subject's time and venipuncture-related pain. Thus, the subjects were provided with compensations (10 Jordanian Dinars) for their times spent in the study and ELMA cream will be used before blood sampling to decrease venipuncture-related pain. Moreover, trained nurses will draw blood from participants, following the Blood Sampling Guideline of the European Federation of Clinical Chemistry and Laboratory Medicine, 2017.

Potential benefits of the measurement activities and intervention to study subjects included increased knowledge and awareness about their health and mind-body modalities. For society, potential benefits included a greater understanding of the effects of mind-body modalities on stress reduction and the potential improvement of the study population's health. In this study, potential benefits are believed to exceed risks.

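### The modality comparison rests on unadjusted post hoc t-tests over about 14 scores, with no key outcome per domain, no planned modality contrast and no multiplicity rule

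*Combined protocol and SAP*

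**What the plan says.** **Aim.** The Introduction states: "This study will investigate and compare the empirically defined effects of three common mind-body modalities", and names cognitive, emotional and physical health as the domains.

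**Background theory.** The Introduction sets out two opposing views. One holds that all relaxation techniques act alike. The other, the specificity theories, holds that each has its own benefits. As examples of the second view it gives one statement per technique. The first, for the physical domain, reads "PMR, classified as somatic technique, works better to improve physical health". The second, for the emotional domain, reads "Guided imagery is more effective in improving emotional health". The third, for the cognitive domain, reads "Mindfulness meditation is categorized as a cognitive technique, which should work better for improving cognitive health". It then says that research support is conflicting. Significance of Study says the results may support the specificity theories, and hopes that they will "give clinicians and relaxation trainers tools for intelligently tailoring" techniques to students' symptoms or health problems.

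**Analysis.** The Statistical Analysis section has three sentences on the hypotheses:
- The main test: "One-way- ANOVA will be used to test the study hypotheses".
- The follow-up, with the final measurement as its time point: "Post hoc t-tests will be run to examine if the study groups will be significantly different on the dependent variables".
- The provision for adjustment: "In case of having confounding effects of some variables, ANCOVA will be used".

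The protocol lists no formal hypotheses. It names no primary outcome, no particular pair of groups and no adjustment for multiple tests. It does not say whether the t-tests depend on a significant F.

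**The concern.** The four groups include control, so a significant F does not say whether the modalities differ from one another. That question is left to the t-tests, which range over every dependent variable without error control. If the three modalities work equally well, a significant difference between two of them on some score is then likely to appear by chance. Advice to match a technique to a student's symptoms, which is the use the protocol has in mind, could rest on such a result.

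**Working it through.** **Inputs from the protocol.** Four groups, alpha 0.05, power 0.80, f = 0.25, N = 180 (Determination of Sample Size) and equal allocation (Procedure), so 180/4 = 45 per arm. Scores, from Instruments:
- cognitive, 3: executive function, mindfulness, perceived stress;
- emotional, 5: depression, anxiety, three DASS-21 subscales;
- physical, 6: PHQ-15, cortisol, melatonin, C-reactive protein, interleukin (counted once), leptin.

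The total is 3 + 5 + 6 = 14, or 12 if DASS-21 is counted once.

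**Assumptions, which the protocol does not supply.** Two-sided tests, normal data with unit SD, correlation between outcomes from 0 to 0.7, and the same effect against control on every score.

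**The plan's own figure.** λ = f²N = 0.0625 × 180 = 11.25. On 3 and 176 df the power is 0.804, so a one-way four-group F reproduces 180. The sample size section names a mixed-design repeated-measures ANOVA; that mismatch is a separate matter.

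**What the F can separate.** If one group differs from three equal groups by d, then f = d√3/4, so d = 4 × 0.25/√3 = 0.577 SD. This is the same whether the odd group is control (all three modalities equally better) or one modality (only that one works). The F rejects in about 80% of trials in both cases.

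**One outcome, modalities equal.** Each active-versus-active t-test has standard error √(2/45) = 0.211 SD and 88 df. Three independent tests would give 1 − 0.95³ = 14.3%. Because the arms are shared, simulation (200,000 trials) gives 12.2%. Among trials with a significant F, with all modalities 0.577 SD better than control, it is 14.7%.

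**Fourteen scores, modalities equal.** There are 14 × 3 = 42 active-versus-active tests, out of 14 × 6 = 84 in all. With independent scores, 1 − (1 − 0.122)¹⁴ = 84%; with 12 scores, 1 − (1 − 0.122)¹² = 79%. Simulation (10,000 trials per cell) gives the following, the low end at correlation 0.7 and the high end at 0:

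| t-tests run | Effect of each modality v control | Any modality difference | Theory's favoured modality beats at least one rival in its own domain |
|---|---|---|---|
| Always | any | 50–84% | 32–48% |
| Only after significant F | 0 | 22–42% | 14–20% |
| Only after significant F | 0.3 SD | 39–69% | 24–35% |
| Only after significant F | 0.577 SD | 48–83% | 31–46% |

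As a check on the last column, 14 × 2 = 28 own-domain tests, each with a 2.5% chance in the favoured direction, would give 1 − 0.975²⁸ = 51% if independent. Shared arms bring this to 48%.

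**Stricter criterion.** The favoured modality beats both rivals on some score in its domain in only about 4–7% of trials, or 3–6% if the t-tests follow a significant F.

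**Effect of restricting and adjusting.** Take one outcome per domain and the six comparisons of the theory's favoured modality with its two rivals. False hits in either direction fall from 20–25% unadjusted to 4–5% with Holm. In the predicted direction only, they fall from 13% to about 2.4%.

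**The case against.** **The mapping belongs to the cited theories.** This stands. A reader might infer that the protocol itself predicts which modality is best in which domain, and that a third to a half of trials would falsely confirm the prediction. The documents do not support that. The mapping is given as an example of what specificity theories claim, beside an opposing theory and a statement that the evidence conflicts. The 32–48% behind such a headline counts beating just one rival on any one score, with no gate on the F. A claim to be best in a domain means beating both rivals, and the rate for that is 4–7%.

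**Modality comparisons are not absent.** This also stands. The t-tests compare the study groups at a stated time and would presumably include the modality pairs. On one outcome they are informative: at least one modality difference appears in 12% of trials if the modalities are equal, against 89% if only one works, by 0.577 SD. What is missing is a choice of outcome, a planned set of comparisons and an error rule.

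**Post hoc usually means after a significant F.** This is a natural reading, though the section does not say it. Controls also sit with eyes closed and relax (Control Group), so small effects against control are plausible and the lower gated rows of the table may be the relevant ones. For one outcome, with all four groups equal, the gate holds error at 5%. It does not protect equal modalities once control differs, because the F is then significant for another reason. Nor does it protect across scores.

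**Conclusion.** The concern holds, as a shortcoming that should be corrected. Under the written plan, claims that one modality outperforms another are unreliable: with truly equal modalities, some unadjusted difference appears in 50–84% of trials over 14 scores, and even the most favourable gated case leaves 22–42%. These figures rest on 45 per arm, two-sided 0.05, outcome correlations of 0 to 0.7, and a count of 14 scores. Counting DASS-21 once lowers the rates somewhat without removing the problem. Because no hypotheses are listed, the study hypotheses that the ANOVA is to test have no defined content. The point does not extend to saying that the protocol adopted the theories' mapping, or that a false finding of best in its domain is common.

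**What to change.** Amend the Statistical Analysis section before outcome data are seen:

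1. Name one outcome per domain from those already collected. The choice is the sponsor's.
2. Pre-specify baseline-adjusted (ANCOVA) comparisons among the three active arms at the end of the intervention, with estimates and intervals, and without waiting for a finding of confounding. If the sponsor adopts the theories' mapping as its hypothesis, use six comparisons: PMR v GI and MM on the physical outcome, GI v PMR and MM on the emotional, MM v PMR and GI on the cognitive. Otherwise use all nine (three pairs in three domains).
3. Choose one error rule in advance. For claims that one modality is better than another, apply Holm over the chosen set. For the claim of best in its domain, require that the modality beats both others, with Holm over the three domains.
4. Treat other scores and the mid-point as exploratory for the modality question, and keep modality versus control as a separate question.
5. State that own-domain superiority alone does not establish specificity, since a modality that is best everywhere would also show it, and report all pairs in all domains. That display is descriptive and does not test specificity.

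**Cost.** No new data, but power is limited and should be stated. Without baseline adjustment, one comparison at 0.05/6 has about 11%, 22% and 38% power at 0.3, 0.4 and 0.5 SD; beating both rivals at 0.05/3 has about 6%, 16% and 31%. If baseline and final scores correlate at 0.5 or 0.7 (assumed), the 0.5 SD figures become 52% or 73% for one comparison, and 46% or 70% for beating both. With nine comparisons Holm starts at 0.05/9, so power at that first step is lower than with six.

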This study uses a blocked randomized controlled design. The study subjects will be selected using a convenience sampling method. When selected, the subjects will be randomly assigned to either one of the 4 study groups using a stratified random strategy (stratifying variable= academic year of study). The study groups (PMR, MM, GI, Control group) will received 5 30-minute weekly sessions of their assigned intervention over 5 weeks. However, there will be a 4-hours workshop explaining the purposes and techniques of the study interventions before introducing the actual session. The subjects will be asked and encouraged to practice their assigned intervention for 30 minutes daily at home. The dependent variables will be measured three times for the 4 groups: at baseline, at the middle (after the second session), and at the end of intervention.

Participants

Participants are undergraduate nursing students who will be selected using a stratified random sampling method from Jordan University of Science and Technology. Jordanian undergraduate nursing students will be asked to participate in the current study if they are at least 18 years old and taking a clinical course. Exclusion criteria include students who are 1) practicing of any type of relaxation techniques, such as yoga, guided imagery, meditation, cognitive behavioral therapy, or 2) taking hypnotics, sedatives, anxiolytic, anti-depressant, anti-inflammatory drugs.

Determination of Sample Size

Using G* Power software 3.1, mixed-design (within groups-between groups) repeated measures ANOVA, an alpha of .05, a power of 0.8, the number of measurements of 3, the number of groups of 4, and a moderate effect size of 0.25, the sample size of 180 was generated. A 15 % attrition rate was reported in a previous study with variables similar to the present study [14]. Considering an expected attrition rate of 15 %, the required final total sample size 210.

Intervention

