Control Group. Participants in the control condition will be instructed to sit with their eyes closed during the intervention periods. Participants in the control group will follow an identical time period as the experimental groups. For instance, when the experimental groups will practice for 30 minutes, the participants in the control group will be asked to sit with eyes closed and relax for 30 minutes.

Procedure

First, approvals from the JUST institutional review boards will be obtained. After that, a translation from English to Arabic and pilot testing of the English versions of the scales used in the current study will be performed. The scales used in the study will be introduced for 30 Jordanian undergraduate nursing students, and then the construct validity, reliability (internal consistency), readability of these scales will be examined.

After taking the permission of the dean of nursing college and class's instructors, the PI will visit students in their classrooms. As the lecture finishes, The PI will announce the

title and objectives of the study and ask the students who would like to participate to contact him using a business card including the PI's contact information (his name, phone number, and email) given for each one. The contact information will be used only for the purpose of the study. The PI will arrange an initial meeting to meet with students who would like to participate on another day in a private room at the university. At this meeting, the PI will inform the students the study's objectives, risks, benefits, and confidentiality and answer questions that they have about the study. Also, they will be assured that they have the full right to refuse or discontinue the participation at any time and that such refusal or discontinuation will not affect their academic achievements in any way. If agree to participate and eligibility criteria are met, informed consent will be obtained at the meeting. After that, the participants will be randomly assigned equally to the study groups using a stratified random assignment method (stratifying variable= academic year of study). Finally, dates and times for sessions will be set up and sent to the participants using their e-mails.

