Various strategies will be followed to decrease measurement errors potentially affected by variations of data collection procedure. For example, filling out the questionnaire may be stressful for some subjects and, in turn, influences objective measures. Therefore, the self-reports measures will be completed after taking the objective measures such as biological markers. Also, all study measurements in the intervention and control groups will be undertaken in the same conditions (i.e., same room temperature and environment) by well-trained nurses as much as possible. The ELISA protocol, including blood sampling will strictly be followed. The neurotransmitters/hormones will be measured between 8:30 am and 9:30 am for all subjects at sitting position. Drinking coffee, tea, and having should be avoided 6 hours before the measurement of neurotransmitters/hormones. To decrease venipuncture-related pain during blood sampling, EMLA cream will be used, which has been found effective in decreasing venipuncture-related pain in different populations [17]. In addition, quiet environments, free from distraction, will be maintained with a “Do Not Disturb” sign on the door of the rooms during the intervention and data collection.

Instruments

The study data will be collected using self-reported and physical measures. For the self-reported variables, the study will use a self-reporting questionnaire in 6 main parts. The first part includes questions about smoking behaviors and demographic characteristics including: age, religion, gender, marital status, academic year of study, nationality, history of medical or psychiatric illnesses, and smoking behaviors. The second part includes scales used to measure cognitive responses such as executive function, mindfulness, and perceived stress.

The third part involves scales used to measure emotional health such as anxiety and depression. The fourth part includes a scale used to measure physical symptoms. The fifth part includes scale used to measure coping behaviors. The sixth part includes a scale used to measure fear-related injection. The seventh part includes open-ended questions focusing on the students' experiences of practicing their assigned intervention. The last three parts will be measured to examine the confounding effects of coping behaviors and fear associated with blood sampling on the study outcomes.

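### No primary outcome and no multiplicity control over about 14 outcomes: if the modalities are equal, at least one false modality difference has a 21–41% chance with no benefit, and more if they work

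*Combined protocol and SAP*

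**What the plan says.** The Introduction sets two theories against each other. In one, the "relaxation response hypothesis states that all stress-reduction techniques have the same impact on health outcomes". In the other, "the specificity theories of relaxation claim that each approach of relaxation is associated with different health benefits", with a predicted pattern: PMR for physical health, mindfulness for cognitive health, and "Guided imagery is more effective in improving emotional health". The aim follows: "This study will investigate and compare the empirically defined effects of three common mind-body modalities".

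The Instruments section and the outcome sections after it list the dependent variables:

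- Cognitive (3): "scales used to measure cognitive responses such as executive function, mindfulness, and perceived stress".
- Emotional (5): PHQ-9, a seven-item anxiety scale, and three separately scored DASS-21 subscales.
- Physical (6): PHQ-15 and five serum biomarkers.

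That makes 3 + 5 + 6 = 14, or 12 if DASS-21 is taken as one total. Some of the lists are open-ended, so the count is approximate. No outcome is called primary.

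Statistical Analysis plans one-way ANOVA for the hypotheses, followed by: "Post hoc t-tests will be run to examine if the study groups will be significantly different on the dependent variables", at the end of the intervention. It names no correction, hierarchy, significance level or target error rate. An alpha of .05 appears only under Determination of Sample Size.

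**The concern.** Four groups give C(4,2) = 6 pairs per outcome, and 3 of these compare one modality with another. Over 14 outcomes that is 14 × 3 = 42 modality comparisons, all unadjusted.

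Running the t-tests only after a significant ANOVA would not protect these comparisons. If the modalities beat control, the control arm makes the ANOVA significant, and three modality-versus-modality t-tests then run at 0.05 each.

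The error at issue is the one that matters most here. If all techniques work equally well, a false difference between them would be read as support for specificity. The protocol also intends its results to guide which technique is offered to which student.

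**Working it through.** **The plan's own figure.** A one-way ANOVA with 4 groups, f = 0.25 and N = 180 has noncentrality 180 × 0.25² = 11.25. Power from the noncentral F(3,176) at 0.05 is 0.804, so the 180 reproduces as a one-way ANOVA. The mixed design named in the sample-size section does not give 180 at usual settings: at a correlation of 0.5 its between-groups test needs 124. That is a separate matter and does not affect this point.

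**Inputs from the documents.** Equal allocation, so 180/4 = 45 per arm; f = 0.25; one-way ANOVA then t-tests; 14 outcomes; end of intervention.

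**Assumptions.** Normal data; 0.05 for each test; two-sided t-tests only after a significant ANOVA; three modalities with equal true means; a common between-outcome correlation of 0 to 0.7.

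**Size of the benefit.** With three equal modalities a distance d above control, f = d × √3/4. So f = 0.25 means d = 0.25 × 4/√3 = 0.577 SD. Two smaller cases were also run, 0.2 SD and none. The sample-size section gives 0.25 only as an input ("and a moderate effect size of 0.25, the sample size of 180 was generated"), and "the participants in the control group will be asked to sit with eyes closed and relax for 30 minutes", so a smaller contrast is plausible.

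**One outcome.** The chance of a false modality difference is about 4% with no benefit, 6% at 0.2 SD and 12% at f = 0.25.

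**Fourteen independent outcomes.** Using unrounded rates of 0.037, 0.060 and 0.118:

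- No benefit: 1 − 0.963^14 = 0.41
- 0.2 SD: 1 − 0.940^14 = 0.58
- f = 0.25: 1 − 0.882^14 = 0.83

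**Simulation, at least one false modality difference:**

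| True benefit | Corr. 0 | 0.3 | 0.5 | 0.7 |
|---|---|---|---|---|
| None | 41% | 36% | 29% | 21% |
| 0.2 SD, every outcome | 58% | 50% | 41% | 30% |
| f = 0.25, 8 cognitive and emotional scores only | 70% | 64% | 53% | 41% |
| f = 0.25, every outcome | 83% | 75% | 64% | 49% |

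**Sensitivity** (order: none / 0.2 SD / f = 0.25).

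- Twelve outcomes: 20–37% / 28–52% / 47–77%.
- Correlation 0.8: about 16% / 24% / 40%.
- Assumed block structure (scales 0.5, overlapping scale pairs 0.8, biomarkers 0.1, scales with biomarkers 0): 35% / 49% / 73%.
- 52 per arm: 22–42% / 31–59% / 49–83%.
- No ANOVA gate: about 48–84% at every level of benefit.
- Only false differences in the Introduction's predicted direction: 13–19% / 18–28% / 30–46%.

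**Partial remedies, over the same correlations.**

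- Tukey within each of the 14 outcomes and nothing else: about 14–33% across the scenarios.
- Bonferroni on the 14 ANOVAs with unadjusted t-tests: 40–73% at f = 0.25.
- Three named primaries with gated t-tests kept: 24–32% at f = 0.25.

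**The case against.** The strongest reply is that the large percentages rest on choices the documents do not make. Correlation 0 supplies every upper bound and is unrealistic for overlapping scales. A benefit of f = 0.25 on all 14 outcomes is extreme. For a single outcome the error is near nominal at 4% and 6% in the two milder cases, so most of the inflation there comes from treating 14 outcomes as one family. The Introduction poses three domain questions with a predicted pattern, and one isolated false difference is not that pattern. On average only about 14 × 0.037 = 0.5 outcomes would show one with no benefit, and 14 × 0.060 = 0.8 at 0.2 SD. The model is also narrower than the protocol, which sizes the trial on a repeated-measures ANOVA and allows ANCOVA for confounding.

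Much of this stands as a limit on precision: the percentages are illustrative, and the block-structure values are a fairer central guide than the upper bounds. It does not remove the gap. The mildest case computed (predicted direction only, no benefit, correlation 0.7) is still 13%. The gate favours the plan, and so does counting only the final time point. The words post hoc do not imply an adjustment when the tests named are t-tests. Nor is the trial described as exploratory: the ANOVA is said to test the study hypotheses.

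**Conclusion.** The concern holds and needs fixing before analysis. That no primary outcome is named and no multiplicity rule is given is certain from the text. If the modalities are equal, the plan gives a false modality difference well above 5% of the time in every scenario computed: 21–41% with no benefit, 30–58% at 0.2 SD, and 49–83% only if every outcome improves by f = 0.25. These ranges assume 14 outcomes, 45 per arm, 0.05 per test, ANOVA-gated t-tests and between-outcome correlations from 0.7 down to 0. The ordering by size of benefit depends on the gate; without it, all three cases sit at about 48–84%. If a primary or a correction is chosen only after the data are seen, the results could drive the choice.

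**What to change.** Amend Statistical Analysis before any analysis, as follows.

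1. The investigators name one primary outcome for each domain: cognitive, emotional and physical.
2. Replace the post hoc t-tests with Tukey or Holm-adjusted pairwise comparisons, and state one rule:
   - Holm across the three primary ANOVAs, with Tukey at 0.05 within each significant one. This leaves about 6–8% between-modality error at f = 0.25 and 4–5% at 0.2 SD.
   - Tukey at 0.05/3 for each primary, if strict 5% control is wanted. This leaves 2–3%.
3. Label all other scales and biomarkers secondary, reported with confidence intervals and no confirmatory claim.

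Within this scheme steps 1 and 2 are both needed, since naming three primaries alone leaves 24–32% at f = 0.25. Other rules would also serve if fixed in advance. A single primary with Tukey at 0.05 leaves about 3%, with power of about 0.56 for one modality-versus-control pair. Bonferroni over all 42 modality comparisons (0.05/42) leaves about 3–5% without naming a primary.

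The cost is wording and a restated power, with no added participants. At N = 180 and f = 0.25, ANOVA power for one outcome falls from 0.80 at 0.05 to 0.66 at the strictest Holm step (0.05/3). It averages about 0.74–0.75 under Holm if all three primaries have f = 0.25. Power for one modality-versus-control pair (0.577 SD) falls from about 0.71 with gated t-tests to 0.54 (Holm plus Tukey) or 0.40 (Tukey at 0.05/3).

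Adjusting for the baseline measure already planned would recover some of this. The effective difference becomes 0.577/√(1 − r²), which is 0.605, 0.667 and 0.808 SD at assumed baseline-to-end correlations of 0.3, 0.5 and 0.7. Pair power is then about 0.59, 0.70 and 0.89 (Holm plus Tukey), or 0.46, 0.57 and 0.80 (Tukey at 0.05/3).
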